4.2.2.3 Handling of Dropouts and Missing Data

Missing S-K c-lab values will be replaced as described in Section 3.3.5.

4.2.2.4 Primary Analysis of Secondary Endpoints (OLP)

Descriptive statistics will be presented for S-K levels at baseline, OLP Day 1 (1, 2 and 4 hours post first dose) and OLP Day 2 (pre-dose and 1 hour post the first dose in the day), OLP Day 3 (pre-dose) and end of OLP, including the mean change (absolute and percent change) from baseline. In addition, a box plot of S-K values by timepoint will be presented.

Similarly, descriptive statistics tabulating the proportion of subjects who achieve normokalemia at each of the timepoints specified above will be presented.

Proportion of subjects who achieve normokalemia

The observed proportions of subjects achieving normokalemia at 24 hours (OLP Day 2) and end of OLP will be provided along with 95% two-sided Clopper-Pearson exact confidence intervals.

Exponential rate of change

The exponential rate of change in S-K levels will be derived from a longitudinal mixed model (SAS PROC MIXED, see Section 3.3.5) of log-transformed S-K levels during the OLP. Measurements up to and including 24 hours post-dose will be used as the response variable. The model will include OLP baseline eGFR, OLP baseline S-K values as well as age (<55, 55-64, >64 years), time (in hours) and baseline binary indicators for RAAS inhibitors, chronic kidney disease, heart failure, and diabetes mellitus as fixed effects terms. A random intercept and slope (for time) will be used in the model. The exponential rate of change will correspond

to the estimate of the parameter describing the SK decline over time, i.e. the slope in terms of log SK. It will be presented with corresponding standard error, 95% confidence interval and p-value.

Mean change (absolute and percent change) from baseline

For changes and percent changes from baseline in S-K levels at 24 hours (OLP Day 2) (and end of OLP, one sample, two-sided t-tests will be applied to test the null hypotheses that the means are equal zero. The estimates, corresponding SD, 95% 2-sided CI and p-values will be presented.

Time to normalization in S-K values

The time to normalization in S-K levels will be summarized using Kaplan-Meier life table curves and associated 95% CI points will be provided at 1, 2, 4, 24 and 48 hours post first dose of IP.. All S-K assessments during OLP will be used.

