4. STUDY PLAN AND TIMING OF PROCEDURES

Study Visit	Visit 1	Visit 2	Visit 3	Visit 4 ⁸	Rand. Visit	EOS ¹⁰	
Initial Phase Day	Pre- screen ³	Screen	Day 1 ¹⁴	Day 2 ¹⁴	Day 2 or 3 ¹⁴	Day 9 (+ 1d)	
Accepted visit window during prolonged public holidays ¹⁸						Day 4-16	
Written informed consent	Х	Х					
Eligibility criteria	Х		\mathbf{X}^{11}		Х		
Demographics	Х	Х					
Medical History			\mathbf{X}^{11}				
Physical exam including weight			X ^{11, 15}		X ¹⁵	X^{15}	
Access IVRS/IWRS		Х	Х		X^{12}		
Study drug (IP) dispensation			Х				
Study drug (IP) administration			Х	Х			
ECG			\mathbf{X}^{11}	Х	Х	Х	
Vital signs			\mathbf{X}^{11}		Х	Х	
Concomitant medications			X^{11}	Х	Х	Х	
Adverse events			X^{16}	Х	Х	Х	
Serious adverse events	X^{17}		Х	Х	Х	Х	
Potassium ^{6, 13}	X^2		X^4	X^5	X ⁹	X^9	
Clinical chemistry ^{1,6}			X ¹¹		Х	Х	
Hematology ^{1,6}			X^{11}		Х	Х	
Urinalysis ^{1,6}			X ¹¹		Х	Х	
Urine HCG			X ^{7,11}			X^7	
IP Reconciliation						Х	

Table 1Study Plan detailing the procedures: optional Pre-screening, screening and
open-label initial phase

1. Parameters to be measured are detailed in Table 3.

2. Blood potassium will be measured only by i-STAT at the Pre-screening visit (Visit 1).

3. Pre-screening visit is optional. Patients who meet all Pre-screening inclusion/exclusion criteria will be entered into the screening part of the study within 7 days.

4. Potassium will be measured twice 60 (±10) minutes apart within 1 day of first dose administration on the open-label initial phase Day 1(Visit 3) and at 1,2 and 4 hours (±15 min) after administration of the first dose of ZS. Potassium will be measured again at 90 minutes (±15 min) after taking the second dose for patients with i-STAT potassium ≥ 6.1 mmol/L or < 4.0 mmol/L4 hour after the first dose.

- 5. Potassium will be measured predose (0 hour) and 1 hour (±15 min) after the first dose on the open-label initial phase Day 2 (Visit 4). Patients achieving normokalemia (3.5 to 5.0 mmol/L, inclusive) based on the predose potassium value will skip the Visit 4 and will continue on the same day to the Randomization Visit procedures.

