4.3.1 Open-label initial phase Day 1 (Visit 3)

Patients will arrive in the morning, fasting (nothing by mouth except water for a minimum of 8 hours prior to potassium sample collection at the clinic).

The following assessment will be performed:

- Review and confirm the patient's eligibility for the study by assessing inclusion and exclusion criteria listed in Sections 3.1 and 3.2.
- Two potassium samples for assessment, using both i-STAT and the Central Laboratory, will be collected 60 minutes (± 10 min) apart.
- If either i-STAT potassium value is <5.1 mmol/L the patient will be declared a screen failure and withdrawn from the study.
- If both i-STAT values are ≥ 5.1 mmol/L the following samples will be collected:
 - A blood sample for standard assessment of hematology and clinical chemistry
 - Urine for standard assessment of urinalysis parameters including a pregnancy test if the patient is a woman of childbearing potential
- Obtain vital signs (pulse rate and blood pressure)
- Patient medical and surgical history including co-morbidities (over previous 6 months) will be obtained with the review of selection criteria
- Perform 12-lead Electrocardiogram (ECG)
- Perform a complete physical examination including weight, see Section 5.2.2;
- Review and record the concomitant medications and AEs/SAEs

Note: The above procedures should be performed within 1 day of the first administration of study drug and before any IP administration.

Patients who meet all inclusion/exclusion criteria will be entered into the trial and the following procedures will take place:

- The site will access the IVRS/IWRS and the system will assign the patient an openlabel initial phase IP kit
- The first doses of study IP will be administered as a slurry/suspension in water. The patient will be shown/instructed on how to mix and administer the IP
- 1 hour (± 15 min) after dose administration a blood potassium sample (i-STAT and Central Laboratory) will be collected, following which the patient is allowed to break the fast
- Two additional blood potassium samples (i-STAT and Central Laboratory) will then be taken at 2 and 4 hours (±15 min) after dose administration.

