
2. Potassium is measured predose and 1 hour post dose. The predose measure is considered as the 24-hour measurement for all analyses. Patients who achieve normokalemia at 24 hours will proceed to the Randomization (RTP-Day 1) visit.

3. Potassium is measured predose and this measure is considered as the 48-hour measurement for all analyses.

4. End of OLP (24 hours or 48 hours) the latest treatment day of open label initial phase only for patients who complete 24 hours or 48 hours OLP treatment.

5. End of Study Visit (OLP-Day 9) in open label initial phase only for patients NOT entering the 28-day randomized treatment study phase and occurs 7±1 day after the last administration of IP.

6. End of Study Visit (RTP-Day 35) occurs 7±1 day after last planned administration of IP in RTP.

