4.2.2.2 Derivations

See section 3.3.1.1 for definition of baseline for the efficacy endpoints.

Time to normalization is defined as the number of hours from the first administration of IP in OLP to the date-time of normalization = (date-time of normalization – date-time of first IP administration). For analysis of time to normalization, subjects who fail to achieve normalization will be censored at the time of last SK measurement in the OLP.

For analysis of the exponential rate of change, time (in hours) from first dose of IP will be derived as (datetime of SK measurement – datetime of first dose of IP)/3600.

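### Time to normalization is timed by the clock but read at exact hours: the 1, 2 and 4 h estimates can only err downward, and 48 h can err either way

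*SAP*

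**What the plan says.** SAP 4.2.2.2 puts the endpoint on a clock-time scale: "Time to normalization is defined as the number of hours from the first administration of IP in OLP to the date-time of normalization". The same section censors on that scale: "subjects who fail to achieve normalization will be censored at the time of last SK measurement in the OLP". SAP 4.2.2.4 then summarizes the endpoint by Kaplan-Meier, using every potassium assessment in the phase, and "associated 95% CI points will be provided at 1, 2, 4, 24 and 48 hours post first dose of IP". It gives no tolerance around those hours.

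The draws themselves have a tolerance. Protocol Table 1 (note 4) schedules them "at 1,2 and 4 hours (±15 min) after administration of the first dose of ZS", and Protocol 4.3.1 repeats this: "1 hour (± 15 min) after dose administration a blood potassium sample" is collected, and the next two "will then be taken at 2 and 4 hours (±15 min) after dose administration".

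For the later draws, the notes to SAP Table 2 (section 3.3.3) set nominal times. For Day 2: "The predose measure is considered as the 24-hour measurement for all analyses". For Day 3: "Potassium is measured predose and this measure is considered as the 48-hour measurement for all analyses". The windows in Table 2 are in whole days, so nothing there assigns the 1, 2 and 4 h draws to a nominal hour.

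**The concern.** Normalization is seen only when blood is drawn. A patient whose first normal value comes from a 1-hour draw taken at 62 minutes has complied with the protocol, but has an event time of 62/60 = 1.03 h and is absent from the 1-hour estimate. The same can happen at 2 and 4 h.

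At 24 and 48 h the SAP contains two rules that cannot both be followed: the date-time derivation and the nominal times in the Table 2 notes. The choice affects censoring as well as events, because a patient who never normalizes leaves the risk set at the clock time of the last draw.

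Time to normalization is a named secondary endpoint, and the protocol presents rapid onset as a benefit of the drug (section 1.3.1). The tabulated hourly figures should not depend on whether clinics ran a few minutes early or late.

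**Working it through.** The plan states no expected proportion at 1, 2 or 4 h, so there is no figure of its own to reproduce.

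**Inputs**
- Timing tolerance ±15 min at 1, 2 and 4 h: Protocol Table 1 note 4 and section 4.3.1.
- About 280 patients in the open-label phase: Protocol 8.2.
- Cumulative first normalization of 77% by the Day 2 draw and 86% by the Day 3 draw: borrowed from the earlier-study figures in Protocol 1.3.1 and treated as true.
- Cumulative first normalization p1 = 20%, p2 = 52%, p4 = 65% at the scheduled 1, 2 and 4 h draws: illustrative assumption.
- q, the share of draws taken after the nominal minute: not in the documents; anything from 0 to 1 is possible.
- Assumed: no dropout before Day 2, and every patient not normal on Day 2 has a Day 3 draw.

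**1, 2 and 4 h.** With no censoring before Day 2, the Kaplan-Meier estimate is the share of patients whose first normal draw was taken by that clock time:

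KM(1) = (1−q)·p1; KM(2) = p1 + (1−q)·(p2−p1); KM(4) = p2 + (1−q)·(p4−p2).

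| Draw timing | q | KM(1) | KM(2) | KM(4) |
|---|---|---|---|---|
| On time or early | 0 | 20% | 52% | 65% |
| −15 to +5 min | 0.25 | 15% | 44% | 62% |
| Symmetric ±15 min | 0.50 | 0.5×20 = 10% | 20+0.5×32 = 36% | 52+0.5×13 = 58.5% |
| −5 to +15 min | 0.75 | 5% | 28% | 55% |
| All late | 1 | 0% | 20% | 52% |

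Simulation (280 patients, 400 runs) agrees to within about half a percentage point. In the symmetric case the relative loss is 50% at 1 h, 16/52 = 31% at 2 h and 6.5/65 = 10% at 4 h. Each late event has entered the curve by the next read-off, so only new first normalizations at a given draw are at risk.

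**24 and 48 h under the date-time rule.** Before Day 3, 100−77 = 23% are still at risk (about 64 of 280). Of these, 9/23 = 0.391 normalize at the Day 3 draw and the rest are censored at it.
- *Draws up to 1 h late.* Nothing from that day is counted at its read-off: 65% at 24 h and 77% at 48 h.
- *Draws from 1.5 h early to 1 h late.* A share 1.5/2.5 = 0.6 are taken by the read-off. At 24 h: 65+0.6×12 = 72%. At 48 h, survival is about 0.23×(1−0.6)^0.391 = 0.23×0.70 = 0.16, so 84%.
- *Draws 0 to 2 h early.* At 24 h: 77%. By 48 h all 64 Day 3 draws have been taken, with events and censorings interleaved, so the risk set empties. Expected survival is 0.23 × ∏(1−0.391/m), m = 1 to 64, = 0.23×0.13 = 0.03, so 97%.

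Simulation gives 65/77%, 72/84% and 77/97% for the three cases. With scheduled times for events and censoring it returns 20/52/65/77/86%, the assumed values.

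**The case against.** The strongest reply has four parts.

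1. **The curve is not wrong.** A Kaplan-Meier curve on actual times correctly places each normalization when it was observed. This stands. A reader might infer that the whole onset curve is in error or that late samples are lost. Neither is so at 1, 2 and 4 h: only the tabulated read-offs are affected.
2. **The size is unknown.** A reader might infer that about half the samples due at each early hour go uncounted. That requires timing symmetric about the hour, and the documents give a permitted window, not a distribution. If clinics draw on time or early, the early loss is zero. This stands, so the size can only be given as a range.
3. **The Table 2 notes already settle 24 and 48 h.** A programmer could apply them, so this is a conflict between two SAP sections, not a demonstrated error. That is fair, but the conflict has to be resolved because the results differ. It can also be argued that the Day 1 dose follows two draws an hour apart and other procedures, so the later morning draws probably precede 24 and 48 h. That is an inference. It would protect the 24 h figure, but it is the pattern that inflates the 48 h figure.
4. **The information exists elsewhere.** SAP 4.2.2.4 also tabulates normokalemia by scheduled time point, unaffected by clock time. This limits the harm. The table is a different quantity, however: status at a visit, not cumulative first normalization. A reader might take a disagreement between the two as proof of error, but they can differ legitimately even with perfect timing.

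**Conclusion.** The point holds in limited form. As written, the SAP combines clock-time events with exact-hour read-offs and has no nominal-time rule for the 1, 2 and 4 h draws. Relative to the scheduled samples those estimates can only be too low, with the largest relative loss at 1 h: from none to all of the 1 h proportion in principle, and half of it under symmetric timing. The percentages rest on assumed scheduled proportions and assumed timing. The direction at 1, 2 and 4 h needs only the absence of censoring before Day 2.

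At 24 and 48 h the defect is a conflict between SAP 4.2.2.2 and the Table 2 notes. A reader might infer that the error always runs against the drug. At 48 h it does not: for an assumed true 86%, the date-time rule gives 77% to 97% in the cases tried.

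The consequence is confined to a single-arm descriptive summary that is not in the testing sequence of SAP Table 3. No test, sample size or confirmatory conclusion is affected. The change should still be made, because the endpoint is a named secondary and the correction is simple.

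**What to change.** Add to SAP 4.2.2.2 that, for the Kaplan-Meier analysis of time to normalization, scheduled times are used for both events and censoring: 1, 2, 4, 24, 25 and 48 h after the first dose. Include a scheduled time for the sample taken 90 minutes after dose 2 in patients kept in clinic. Dose 2 is due about 4 h after dose 1, so this is about 4 + 1.5 = 5.5 h. Without it, the rule would not cover every assessment that SAP 4.2.2.4 says is used. This also brings the derivation into line with the Table 2 notes.

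Reading the curve at the window ends (1.25, 2.25 and 4.25 h) would recover the early proportions. It would not cure the Day 3 censoring problem, and the documents give no clock window for the Day 2 and Day 3 predose draws. Scheduled times are therefore preferable.

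The cost is a sentence in the SAP and a small programming change, with no new data.

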4.2.2.5 Sensitivity Analyses of the Secondary Endpoint

Not applicable.

4.2.2.6 Supplementary Analyses of the Secondary Endpoint

Two supplementary analyses, aiming at evaluating the impact of use of disallowed medication, will be performed. The first one will consider the proportion of subjects that achieved normokalemia at 24 hours (OLP Day 2) and at the end of OLP without use of rescue medication. That is, the analysis of the proportion of normokalemic subjects described above will be replicated, with endpoint re-defined so that a subject is considered to be a responder only if they achieved normokalemia and did not use disallowed medications prior to the relevant timepoint, which would constitute a composite strategy with respect to the intercurrent event of disallowed medication usage.

The second analysis will exclude all SK measurements in the OLP obtained post usage of disallowed medications and replicate the analysis of the mean change in SK at 24 hours (OLP Day 2) and at the end of OLP as compared to baseline on the resulting data. This would constitute a hypothetical strategy with respect to the intercurrent event of disallowed medication usage, with the hypothetical scenario being that disallowed medications are not available to subjects.

Disallowed medications are listed in Appendix B: Disallowed Medications.

A third supplementary analysis will be performed assessing the exponential rate of change up to 48 hours post-dose. The exponential rate of change in S-K levels will be derived from a longitudinal mixed model (as described in Section 4.2.2.4) of log-transformed S-K levels

during the OLP. Measurements up to and including 48 hours post-dose will be used as the response variable.

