1.3 Benefit/risk and ethical assessment

Hyperkalemia is common in patients with chronic kidney disease, or heart failure, particularly when treated with renin angiotensin aldosterone system inhibitors (RAASi). Mortality risk with hyperkalemia parallels the magnitude of potassium elevation.

Figure 1 Multivariable-adjusted mortality by serum potassium level in a cohort of 55,266 patients with eGFR <60 ml/min per 1.73 m2 during median follow up 2.76 years (Lou J et al 2016)

For acute treatment, intravenous glucose/insulin and inhaled beta-adrenergic agonists drive potassium into cells. Potassium can be removed from the body by dialysis or with non-absorbed polymers which non-selectively bind potassium and are excreted. Polymers do not lower potassium rapidly and cause significant gastrointestinal (GI) side effects (colonic necrosis, bowel obstruction, GI bleeding, ischemic colitis, perforation), bind to many oral medications and to other cations, lowering magnesium and calcium levels. Thus, an unmet need remains for safe, rapid, and an effective treatment for hyperkalemia.

Sodium zirconium cyclosilicate (ZS) is a non-absorbed, inorganic crystal that selectively exchanges hydrogen and sodium cations for potassium in a dynamic process throughout the upper and lower gastrointestinal tract. Bound potassium ions are excreted from the body. ZS is

a white, insoluble, powder provided in 5g and 10g sachets to be suspended in water for oral administration.

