7.7 Concomitant and other treatments

All concomitant medications taken by the patient from 7 days prior to the open-label initial phase Day 1 until the 28-day randomized treatment study phase Day 35(EOS), or the end of the study (7 ± 1 days after the last dose of IP) for patients, will be recorded.

Whenever possible, all blood draws collected prior to meals should be collected prior to any insulin/insulin analog treatment. From the open-label initial phase Day 1 through the 28-day randomized treatment study phase Day 28, the time of dosing with insulin/insulin analogs must be recorded when IP is administered in the clinic.

During the study, the patient cannot receive alternative treatment for hyperkalemia while taking IP. If dosing with IP is discontinued or the patient has completed dosing, the patient may receive alternative treatment for hyperkalemia if clinically indicated prior to completing the EOS visit. Any alternative treatment administered after the end of IP administration and prior to the EOS visit must be recorded in the concomitant medication eCRF page (and as AE if applicable).

In addition to therapies for hyperkalemia also other drugs with World Health Organization Anatomic Therapeutic Chemical classification code V03AE, i.e., potassium binders such as sevelamer, calcium acetate, and lanthanum carbonate, are prohibited to be taken while receiving IP, as the effects of potassium binding drugs may effect safety laboratory assessments.

Changes to RAAS inhibitor and/or diuretics (including adding a new, changing the dose or discontinuation or switching of RAAS inhibitor and/or diuretics) during the study are prohibited. If clinically indicated to change the RAAS inhibitor and/or diuretics, the patients should discontinue study medication.

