4.1.6.2 Presentation

Medical history and surgical history are grouped by MedDRA system organ class and preferred term and are summarized by System Organ Class (SOC) and Preferred Term (PT), for all subjects in FAS-OLP and in FAS-RTP.

They will be listed for all subjects enrolled and summarized respectively for the FAS-OLP and FAS-RTP. This listing will be presented sorted by treatment group, subject ID, and date/time of the event.

4.1.7 **Prior and Concomitant Medications**

4.1.7.1 **Definitions and Derivations**

Medications will be classified according to the latest version of the WHO Drug coding dictionary. Prior medication is any medication that started and stopped prior to treatment with investigational product. Concomitant medication is any medication that is taken concurrently with investigational product regardless of the start date of the medication. Concomitant medications include allowed and disallowed medications taken by the subjects during the respective phases (i.e. a medication can be concomitant for the OLP but not RTP, or RTP but not OLP). Missing medication start and stop dates will be imputed according to Section 3.3.1.4.

For the definition of disallowed medications, see Appendix B.

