7.2 Appendix B: Disallowed Medications

Disallowed medications in the study broadly consist of two classes: potassium binders and RAASi / diuretics. For the former, any use of while on IP is to be considered as an instance of disallowed medication usage. For the latter, as per the CSP, the addition of a new RAAS inhibitor and/or diuretic, or change of the dose, discontinuation, or switch of these drugs, is to be considered as an instance of usage of disallowed mediation.

The exact method by which such instances of usage can be identified in the database will be documented separately.

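### SAP Appendix B omits the protocol's general ban on other hyperkalaemia treatment while on study drug, so the supplementary disallowed-medication analyses, including open-label response without rescue, do not fully measure what they claim

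*SAP*

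**What the plan says.** **Protocol 7.7** sets three restrictions.

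- A general ban: "During the study, the patient cannot receive alternative treatment for hyperkalemia while taking IP".
- Potassium binders, introduced as an extra group: "In addition to therapies for hyperkalemia also other drugs with World Health Organization Anatomic Therapeutic Chemical classification code V03AE".
- Any change to RAAS inhibitors or diuretics.

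**SAP Appendix B** has two groups: "Disallowed medications in the study broadly consist of two classes: potassium binders and RAASi / diuretics". It leaves to a separate document how such use will be found in the database.

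**The SAP sections that rely on Appendix B** are tied to it by cross-reference. SAP 4.1.7.1 states: "For the definition of disallowed medications, see Appendix B". SAP 4.2.2.6 states: "Disallowed medications are listed in Appendix B: Disallowed Medications". Under 4.2.2.6, "a subject is considered to be a responder only if they achieved normokalemia and did not use disallowed medications prior to the relevant timepoint". The same term defines the intercurrent event in the supplementary analysis of the primary endpoint (4.2.1.5), the second open-label supplementary analysis (4.2.2.6) and the Day 29 composite (4.2.3.4). The SAP uses the word rescue in 4.2.2.6 ("at the end of OLP without use of rescue medication") but does not define it.

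**SAP Appendix A, IPD 6.1** takes its scope directly from protocol 7.7 and includes non-drug therapy.

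**The concern.** These supplementary analyses exist to show whether the result stands once outside potassium-lowering help is accounted for. The SAP names use of disallowed medication as an intercurrent event of concern (4.2.1.1). Appendix B leaves out one of the three groups that the protocol prohibits, and that group includes treatments which the protocol itself describes as moving potassium out of the blood: "For acute treatment, intravenous glucose/insulin and inhaled beta-adrenergic agonists drive potassium into cells".

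The consequence differs by analysis. In the open-label responder analysis, a patient treated in this way who is normokalaemic at the time point is a success under a label that says no rescue was used. That phase has no control arm, so any such error can only raise the reported rate. In the two analyses of potassium values, the affected measurements stay in. In the Day 29 composite, the patient is not set to non-responder.

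The SAP would also be working with two scopes for one idea. The same patient could be listed as having received prohibited therapy and be scored as a responder without rescue.

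**Working it through.** **Step 1. Compare the definitions.**

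| Treatment while on study drug | Protocol 7.7 | SAP Appendix B | SAP IPD 6.1 |
|---|---|---|---|
| Potassium binders (V03AE) | prohibited | counted | counted |
| RAAS inhibitor or diuretic change | prohibited | counted | counted |
| Other treatment for hyperkalaemia | prohibited | not listed | counted |

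The protocol introduces the binder rule as an addition to therapies for hyperkalaemia. It therefore does not replace or exhaust the general ban.

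**Step 2. Follow one patient through the rules.** Suppose a patient on open-label ZS receives insulin/glucose for hyperkalaemia, stays on study drug and has S-K within 3.5 to 5.0 mmol/L at the time point.

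- 4.2.2.6, first analysis: normokalaemic, no Appendix B medication, so a responder.
- 4.2.2.6, second analysis: later values are kept in the mean change.
- IPD 6.1: prohibited therapy, so a deviation.

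In the randomised phase, 4.2.1.5 would not remove the affected values, and 4.2.3.4 would leave a normokalaemic Day 29 response as a response.

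**Step 3. Size in the open-label phase.** Inputs from protocol 8.2: 250 randomised, 90% assumed normokalaemic, about 280 entering.

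- Check of the plan's figure: 250 / 0.90 = 277.8, that is 278, consistent with about 280.
- Effect of one misclassified responder: 1 / 280 = 0.36 percentage points.
- Illustrative starting point: 0.90 × 280 = 252 responders.

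The documents give no rate of use. The counts below only show the arithmetic and are not estimates. Intervals are Clopper-Pearson, the method named in SAP 4.2.2.4.

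| Reclassified | Responders / 280 | Rate | 95% CI |
|---|---|---|---|
| 0 | 252 | 90.0% | 85.9 to 93.3 |
| 1 | 251 | 89.6% | 85.5 to 93.0 |
| 3 | 249 | 88.9% | 84.7 to 92.4 |
| 6 | 246 | 87.9% | 83.4 to 91.4 |
| 14 | 238 | 85.0% | 80.3 to 89.0 |

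Fourteen patients would be 5% of 280 (0.05 × 280 = 14). Nothing in the documents supports a rate that high.

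**Step 4. Direction in the randomised phase.** If such treatment is more frequent on placebo, keeping the treated values lowers mean placebo S-K, and keeping treated responders raises the placebo response. Both shrink the difference from ZS, so the error would work against ZS. If use were more frequent on ZS, the direction would reverse. The documents give no figure for either arm.

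**The case against.** **Such use should be uncommon.** This stands. Protocol 1.1 gives a potassium-binding resin, dietary advice and possibly modified drug treatment as standard care for mild to moderate hyperkalaemia, and Appendix B covers the resin. What remains is mostly emergency treatment, and the protocol takes many of those patients off study drug:

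- An open-label patient above 6.2 mmol/L after the second dose is discontinued (4.3.1).
- A confirmed value above 6.2 mmol/L in the randomised phase leads to discontinuation (3.9).
- Arrhythmias needing immediate treatment, and need for hospitalisation after Day 1 sampling, are exclusions (3.2).
- Dialysis is an exclusion, and starting it is a listed ground for stopping study drug, so it is a poor example here.

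The end-of-open-label time point also exists only for patients who complete 24 or 48 hours of treatment (SAP Table 2, footnote 4). A misclassified patient at that time point must therefore have stayed on ZS. These rules make the case rare but not impossible, because a patient who stays hyperkalaemic below those limits can remain on study drug.

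**The use would be visible anyway.** This also stands. SAP 4.1.7.2 summarises protocol 7.7 medications and procedures in both phases, and the deviation tables carry IPD 6.1. A reader might infer that such treatment would go unreported, but the documents do not support that. Neither table, however, changes responder status or removes a value.

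**Appendix B is worded loosely and defers the detail.** It says *broadly*, and the separate document cannot be seen. That document is described as the method for finding instances of the use just defined. Nothing in the SAP says it adds a third class.

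**A reader might infer that the efficacy conclusion is at risk, or that the ZS effect in the randomised phase is inflated.** Neither follows. The main analyses use a treatment-policy strategy and ignore these events by design. If use is more frequent on placebo, the supplementary error runs against ZS.

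**Conclusion.** The mismatch is real but minor. Appendix B conflicts with protocol 7.7 on what is prohibited, so the open-label label of no rescue promises more than its definition delivers. All four supplementary disallowed-medication analyses inherit the gap, as does the separate disallowed-medication summary in 4.1.7.2.

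The size is about 0.36 percentage points of the open-label rate per misclassified patient, assuming 280 patients. The number of such patients is unknown and probably small. The conclusion assumes that Appendix B is applied as written and that the separate identification document adds no further class. No test in the confirmatory hierarchy changes.

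**What to change.** - Add a third class to Appendix B: any other treatment given for hyperkalaemia while on study drug (protocol 7.7), identified by recorded indication, with insulin given for diabetes not counted. The existing cross-references carry it into 4.1.7.2, 4.2.1.5, 4.2.2.6 and 4.2.3.4.
- In 4.2.2.6, replace rescue medication with disallowed medication.
- Leave IPD 6.1 as it is, since it already refers to protocol 7.7.

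The cost is a short SAP amendment and a blinded review of concomitant-treatment records by indication before database lock. Protocol 7.7 already requires concomitant medications to be recorded, so no new data are needed. The downside is a few queries about indication.
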